6.3 Study Procedures

6.3.1 Study Schedule

WEEK	STUDY VISIT	TIME PER VISIT^
Week 1	Screening visits	2.5 hours
Week 2	ADP Session # 1	12 hours
	Phone visit #1	10 minutes
Week 3	AABM training session #1 + #2	1.5 hours
	AABM training session #3 + #4	1 hour
	AABM training session #5 + #6	1.5 hours
Week 4	ADP Session #2	12 hours
	Phone visit #2	10 minutes
Week 5	Follow-up visit	30 minutes
TOTAL	12 study visits	approximately 31-32 hours

[^]The amount of time is an approximation

6.3.2 Informed Consent

The process of informed consent will minimize undue influence or coercion and offer sufficient time for review. Typically study coordinators will receive thorough training on the correct way to conduct informed consent. On a rare occasion, a study physician or project manager will conduct informed consent. All staff conducting informed consents have at least a Bachelor of Arts or Science in a health-related field and/or have 2 years of research-related experience. Training for the administration of informed consent teaches study staff how to move through the consent, assessing participant's comprehension along the way. A staff member in training will (1) shadow a trained staff member conducting informed consent 2 times, then (2) practices informed consent with other lab members, and finally (3) conducts informed consent with a participant while another trained lab member watches. Once the staff member-in-training satisfactorily conducts informed consent under the supervision of another trained staff member, the staff-in-training becomes authorized to conduct informed consent.

6.3.3 Screening

After consent, participants will be scheduled for screening assessments. The screening phase is accomplished over a total of 1 to 3 visits.

6.3.4 Enrollment

Once a participant has completed all screening/baseline measures and procedures and it has been determined that the participant is eligible and it is safe to participate, then they will be enrolled in the study.

6.3.5 On study visits

Baseline/screening visit 4 hours	Informed consent + HIPAA Participant Locator form Demographics Eligibility form Medical History Physical Exam Lab tests Height/weight Concomitant Medications Columbian Suicide Severity Rating Scale AE Spontaneous Breath alcohol test Structured Clinical Interview for DSM-5 (SCID) Timeline Followback (TLFB) Clinical Institute Withdrawal Assessment (CIWA-AD) Urine Drug Screen (UDS) Barratt Impulsiveness Scale (BIS-11) Alcohol Use Disorders Identification Test (AUDIT) Alcohol Purchase Task (APT) Obsessive Compulsive Drinking Scale (OCDS) Vitals Balloon Analogue Risk Task (BART) Delay Discounting (DD) Iowa Gambling Task (IGT) Salience Task
Phone Visits 1 and 2 10 minutes each	AE Spontaneous Timeline Followback (TLFB)
Human Lab Sessions 1 and 2 12 hours each human lab	Weight AE Spontaneous Concomitant Medications Breath alcohol test Timeline Followback (TLFB) Clinical Institute Withdrawal Assessment (CIWA-AD) Urine Drug Screen (UDS) Blood alcohol level (BAL) Vitals Alcohol Urge Questionnaire (AUQ) Biphasic Alcohol Effects Scale (BAES) Balloon Analogue Risk Task (BART) Delay Discounting (DD) Ratings of Drinking Behavior During the Alcohol Self-Administration Period
AABM/Sham Training Sessions 1-6 30 minutes each visit	Concomitant medications AE Spontaneous Breath alcohol test TLFB (Sessions 2, 5, and 8 only) CIWA-AD AABM/Sham training
AABM/Sham Training Sessions 1 and 6 an additional 1.5 hours	Obsessive Compulsive Drinking Scale (OCDS) Alcohol Purchase Task (APT) Iowa Gambling Task (IGT) Delay Discounting (DD) Balloon Analogue Risk Task (BART)

	Barratt Impulsiveness Scale (BIS-11) Stop Signal Task (SST)
Follow-up Visit 1 hour	Breath alcohol test Timeline Followback (TLFB) Concomitant medications AE Spontaneous Medical Management (MM) Participant End of Study Questionnaire

Assessments at Study Entry and During and After Human Lab Sessions

At Entry:

These are adapted from previous/ current clinical studies at the UCSF/SFVAMC Addiction Research Program.

- Demographic data, will be assessed with data on age, race, socioeconomic status, marital status, educational and occupational levels, and significant medical history.
- A number of safety evaluations are included: Medical history and physical examination; Suicide Risk Assessment: The Columbia Suicide Severity Rating Scale [101]. It is a standard, thorough, frequently used method to screen for suicidal ideation, used by our group in alcohol use disorder clinical trials;
- Clinical Laboratory Tests for Health/Safety Monitoring: Blood samples will be collected for chemistry, liver panel, renal panel and complete blood count (CBC); urine will be collected for urinalysis.
- Structured Clinical Interview for DSM5, (SCID) [96]: the SCID will be used to determine DSM-V diagnosis of current (current year) Alcohol Use Disorder, and the DSM-V current psychiatric diagnoses for anxiety, mood, psychotic, and non-alcohol substance use disorders in order to determine study eligibility.
- Study Physician Review: All health measures, medical history/exams and labs will be reviewed by a study physician to ensure that the subject meets all the eligibility criteria and are ready for randomization
- Alcohol Approach Task (AAT): A way to measure pre-treatment alcohol approach bias tendency. Salience Task: A survey that measures the salience of each stimulus image for participant.

At Entry and at various times throughout the study:

- Clinical Institute Withdrawal Assessment for Alcohol, DSM-IV Version (CIWA-AD): at entry and before each Human Lab Session and at each Follow-up;
- Urine Drug Screen: For opioids, benzodiazepines, cocaine, amphetamines, cannabis, barbiturates: at entry and before each Human Lab Session.
- Breath alcohol concentration (BrAC); at entry and before each Human Lab Session; and during each Human lab Session
- Vital Signs: Temperature, heart rate, and blood pressure will be measured at study entry and multiple times during each Human Lab Session.
- Concomitant Medications Review: at entry and before each Human Lab session: thorough review of all concomitant medications (prescription or over-the-counter) in the past 30 days, as well as those started during the study.
- Concomitant Treatment Log: At Entry and A way to track any type of alcohol treatment at baseline/screening and throughout the study.
- Adverse Effects: Spontaneous: At Entry and at Human Lab Session 1 and 2; Phone visits 1 and 2; AABM Sessions 1-6; 1-wk FU. This form is designed to collect information about adverse health events. We will ask about emergent AEs, follow-up with AEs reported at previous study visits, and ask if there has been a hospital admission since the last study visit.
- Timeline Followback (TLFB): at study entry, then Human Lab Session 1 and Human Lab Session 2. TLFB will be used to calculate standard drinks consumed per week in the past 30 days prior to consent and at the two Human Lab Sessions, and the 1-week follow-up. The TLFB will be used to determine whether subjects meet minimum alcohol consumption criteria at entry. Other substance use will also be collected by TLFB.
- Barratt Impulsiveness Scale (version 11) (BIS-11) [98]: This provides a trait measure of impulsiveness and will be used to characterize the study cohort at study entry.

At AABM Training Sessions:

- Alcohol Use Disorders Identification Test (AUDIT): The AUDIT [97] is valid and reliable self-report measure of alcohol-related problem severity.
- Obsessive Compulsive Drinking Scale (OCDS): At AABM sessions 1 and 6. A questionnaire that measures cognitive aspects of alcohol craving.

- Alcohol Purchase Task (APT): At AABM sessions 1 and 6. A questionnaire uses hypothetical choices regarding alcohol purchases at varying prices to generate several indices of alcohol-related reinforcement.

At Follow-up visit:

- Motivational Enhancement Therapy: at the follow-up visit, research clinician will provide a motivational enhancement session to encourage the non-treatment seeking participants to consider treatment.

Measures of Alcohol Effects:

- Breath alcohol concentration (BrAlc) [99] *at each visit, and multiple times in ADP Sessions 1 and 2*. BrAlc will be measured at each session to detect recent alcohol use with the *Intoximeters Alco-Sensor IV* instrument.
- Blood Alcohol Levels: Human Lab Sessions 1 and 2 (Table 1): Blood samples will be drawn to measure plasma levels of blood alcohol (BAC) during the priming dose and during the alcohol self-administration paradigm. Blood samples will be stored at -4°C and will be analyzed at the San Francisco VA.
- Time-line Follow-back (TLFB): To collect alcohol and drug use in the 90 days prior to entry and all days included in the 11 weeks of the study. TLFB will be used to calculate standard alcohol containing drinks consumed per week in the past 90 days prior to consent and then throughout the 11 weeks of the study. Cigarette and substance use will also be collected by the TLFB.
- Biphasic Alcohol Effects Scale (BAES) [81]: Human Lab Sessions 1 and 2 (Table 1). This 14-item self-report rating scale measures alcohol stimulant/ sedative effects and is used regularly in the Yale ADP.
- Alcohol Urge Questionnaire (AUQ): At study entry; multiple times in Human Lab Sessions 1 and 2 (Table 1); 1-wk FU; 1-mo FU: The AUQ is an 8-item questionnaire assessing *desire, expectation of positive effect, and inability to avoid drinking if alcohol is available*. The AUQ is a reliable and valid scale for the measurement of self-reported alcohol urges. Its brevity and time frame for ratings (i.e. right now) makes it suitable for the ADP.
- Yale Craving Scale (YCS): multiple times during ADP Sessions 1 and 2. A measure of craving for alcohol.
- Ratings of Drinking Behavior During the Alcohol Self-Administration Period: multiple times in Human Lab Sessions 1 and 2. Subjects will be videotaped during the alcohol self-administration portion of ADP 1 and ADP 2. Videotapes will be rated by two independent for the onset and offset of each sip of alcohol. Dependent measures will be constructed including time until the first sip and average time to consume each drink.
- Vital Signs: Human Lab Sessions 1 and 2 (Table 1). These will include heart rate, blood pressure, and skin. The blood pressure cuff will be on subject's dominant arm while the probe of will be attached to the middle finger of the subject's non-dominant arm. These data will be further used to examine the safety of using the study medications during alcohol self-administration.

Neurocognitive Assessments:

The battery was developed to assess performance in cognitive domains commonly affected by heavy alcohol use and contains standardized instruments with good-to-excellent norms administered (~1.5 hours) at AABM sessions 1 and 9. Raw scores will be converted to z-scores. Domain-specific summary scores will be calculated by averaging z-scores of the individual constituent measures. When feasible, alternate forms will be used for repeated administrations.

Domains and constituent measures:

- a) Risk Taking, Decision-making, and Motor/Choice Impulsivity: Balloon Analogue Risk Task⁸⁶; Iowa Gambling Task⁸⁷; Stop-signal⁸⁸, Delayed Discounting⁸⁹;

Cognitive Training – Alcohol Approach Bias Modification (AABM) Training:

Immediately following ADP Session 1, heavy drinking participants will begin to receive 6 sessions of AABM training taking place over 3 weeks. We will use a training version of the Alcohol Approach-Avoidance Task: patients are asked to respond to the format of presented pictures using a joystick (push right-tilted pictures, pull left-tilted pictures), irrespective of the pictures' content. Pushing picture away decreases picture size; pulling a picture closer increases size (zoom effect). There are 2 categories of pictures; 20 different alcoholic and 20 different non-alcoholic beverages (soft drinks). Training effect is achieved by presenting alcohol pictures in push format only and non-alcoholic drinks in pull format only. Two hundred training trials are presented per session (~20 minutes) with a short break halfway through.

Participant Incentives

WEEK	ATTEND STUDY VISIT	TOTAL PER VISIT
Screening	\$55*	\$55
ADP Session #1	\$200 (+ \$24 for tab)**	\$224
Phone visit #1		
AABM 1 + 2	\$50	\$50
AABM 3 + 4	\$40	\$40
AABM 5 + 6	\$50	\$50
ADP Session #2	\$200 (+ \$24 for tab)**	\$224
Phone visit #2		
Follow-up @ 1 Week	\$40 (+ \$50 bonus if attended all study visits)***	\$90
TOTAL		\$733

*At the screening/baseline visit, participants are paid per task they complete. At the end of screening, they will earn \$55.

**Participants will receive \$200 for each ADP Lab Session they complete. They could earn an additional \$24 per ADP Lab Session, depending on how many drinks they consume per session. At each session, participants are offered 8 drinks, each worth \$3. They will receive \$3 per drink for every drink that is not consumed.

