3.2 Purpose of Study/Potential Impact

We will conduct the first pilot trial of AABM effects on alcohol consumption in the human laboratory in non-treatment-seeking, heavy-drinking individuals and the first trial of AABM effects on the Yale Alcohol Drinking Paradigm - a method of rapidly assessing the potential efficacy of putative pharmacologic and possibly behavioral treatments for AUD. Participants will be 12 non-treatment-seeking heavy-drinking male volunteers. After baseline assessment, participants will undergo Human Lab session 1, in which we will administer the Alcohol Approach-Avoidance Task (AAT) (not AABM training) to measure baseline (pre-treatment) alcohol approach bias tendency, and then conduct the ADP to measure baseline alcohol consumption. After Human Lab/ADP Session 1, participants get 2 weeks of a total of 6 sessions of training; they will have been randomly assigned to undergo AABM or a sham training condition. Outcomes will be various measures of feasibility, including recruitment, retention, safety, and adverse effects and assessment of measurement burden, and the tolerability of ADP and AABM interventions

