6. METHODS

The study will consist of the following steps, replicating the Yale ADP methods:

- (1) Recruitment;
- (2) Pre-screening: Brief telephone or in-person to determine eligibility for full screening beginning with establishing non-treatment seeking status;
- (3) Full Screening/baseline visit: 1-3 in-person visits to obtain consent and to evaluate eligibility (e.g. to reject participants with medical conditions): participants who meet *heavy drinking criteria*, and by confirming that the individual is *non-treatment seeking*. If these criteria are met, physical examination and laboratory testing will be conducted. Eligible participants then proceed to the main part of the study, which includes participation in 2 human lab sessions and 6 AABM training sessions.
- (4) Human Lab ADP Sessions 1 and 2: There will be two sessions, Human Lab/ADP Session 1 (Pre-training), and Human Lab/ADP Session 2 (post-training). Alcohol Drinking Paradigm (ADP): After the alcohol cue-induced craving, subjects will be given the opportunity to self-administer alcohol using the ADP. (**Table 1**) Subjects are first given a moderate Priming Drink of alcohol at 11 AM, designed to raise blood alcohol to ~ 0.03 mg%, and are instructed to drink it within 5 minutes. At 1 PM, and again at 2 PM, subjects undergo two 1-hour long alcohol Self-Administration (SA) periods. For each SA period, a tray of 4 beer drinks (each containing an amount of alcohol calculated to increase blood alcohol concentration by 0.015 mg%) will be brought into the Lab room along with a "tab" sheet worth \$12. Participants are told that these 4 drinks will be available for the next 60 minutes, and they can choose to drink or keep the money; each drink will cost \$3. The money will be given by check at the end Human Lab Sessions. This monetary cost for each drink was determined to reliably reflect the trade-off between desire to drink and cost^{20,21}. **The main measure is the number of drinks consumed over the course of two 1-hour-long SA periods**. [name] at Yale University helped to develop the ADP, and it has been adopted by other prominent research groups²²⁻³³.
- (5) Phone Visits 1 and 2: After each Human Lab ADP session, a study coordinator will call the participant to check in by phone.

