6.1.3 Method of Assignment/Randomization

All participants will receive the active AABM training intervention.

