6.1.4 Blinding and Procedures for Unblinding

Not applicable

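### Low priority, cheap to fix: the video raters who time sips before and after training are not masked to session, which leaves an avoidable risk of rater bias in exploratory measures

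*Combined protocol and SAP*

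**What the plan says.** Under Ratings of Drinking Behavior, Section 6.3.5 states "Subjects will be videotaped during the alcohol self-administration portion of ADP 1 and ADP 2". It continues "Videotapes will be rated by two independent for the onset and offset of each sip of alcohol"; the noun is missing in the text available, presumably raters. From these scores, "Dependent measures will be constructed including time until the first sip and average time to consume each drink".

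Section 6, step 4, identifies the two sessions as "Human Lab/ADP Session 1 (Pre-training), and Human Lab/ADP Session 2 (post-training" and describes two one-hour self-administration periods per session, each starting with its own tray. For the paradigm as a whole, "The main measure is the number of drinks consumed over the course of two 1-hour-long SA periods".

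The entry at "6.1.4 Blinding and Procedures for Unblinding" says only that the item does not apply. It gives no reason and does not mention outcome raters. Section 6.1.3, just before it, says "All participants will receive the active AABM training intervention". Section 3.2, by contrast, says of participants that "they will have been randomly assigned to undergo AABM or a sham training condition". Randomisation or sham wording also stands in Section 6 (step 6), Section 6.2.1, and the visit table and physician-review item of Section 6.3.5.

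**The concern.** Having no comparison arm would make blinding to treatment assignment moot, but it would not make assessor masking moot. If every man is trained, the remaining contrast is Session 1 against Session 2, and recorded video can be masked to that even though the participant cannot. As written, a rater may know which session is on screen when judging where a sip starts and stops. If both raters hold the same expectation about the later session, it enters the before-after difference in the timing measures.

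What is at stake is limited but real. The secondary aim in Section 4.3 reaches beyond consumption to behaviours connected with it, and Section 6.3.5 treats the timing variables as dependent measures. The pilot is also meant to try out and refine procedures for later controlled trials (Sections 2.1 and 4.2). Masked scoring is one that such trials would need.

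**Working it through.** The plan has no figure to reproduce: Section 6.4.1 rules out inferential statistics and Section 6.4.2 gives no sample-size basis. The check is a reading of the text plus simple arithmetic.

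**1. Is there masking anywhere?** The video item in Section 6.3.5, the session description in Section 6, the blinding entry in 6.1.4 and the analyses in 6.4 contain no statement that raters are masked to session or that recordings are coded or shuffled. Describing the raters as independent could mean of each other or of the study team. Neither means masked to session.

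**2. Does a second rater help?** Let each rater's before-after change contain a shift, bA and bB. The bias in the averaged change is (bA + bB)/2.
- Both share a shift b: (b + b)/2 = b, so all of it remains.
- Only one has it: (b + 0)/2 = b/2.

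**3. How large might it be?** The document gives no rater error, so b is assumed. If drinking fills the 60-minute period, 4 drinks give 60/4 = 15 minutes (900 s) per drink and 1 drink gives 60 minutes (3,600 s).

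| Shared shift b (assumed) | If one rater only, b/2 | b/900 | b/3,600 |
|---|---|---|---|
| 1 s | 0.5 s | 0.11% | 0.03% |
| 5 s | 2.5 s | 0.56% | 0.14% |
| 10 s | 5 s | 1.11% | 0.28% |
| 30 s | 15 s | 3.33% | 0.83% |

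The percentages use the full shared shift. They rise in inverse proportion if drinks are finished faster than the hour allows. Time to first sip has no denominator in the document. If it is short, the same shift is a larger share of it.

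**4. What would masking involve?** Section 5.3.1 gives 12 men enrolled and up to 15 started. (Section 6.4.3.1 mentions 4 participants and a third session; the counts below follow Sections 5.3.1 and 6.)
- 12 men: 12 × 2 sessions = 24 recordings; × 2 one-hour periods = 48 video hours; × 2 raters = 96 rater hours.
- 15 men, all completing: 15 × 2 = 30 recordings, 60 video hours, 120 rater hours.
- 15 started, 3 leaving after Session 1: 12 × 2 + 3 = 27 recordings.

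The scoring hours are already implied by the plan. Masking adds only the cutting, coding and shuffling of these files.

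**5. What depends on these ratings?** The primary outcomes (5.2.1, 6.2.1, 6.4.3.1) are time to run the study and retention. The secondary outcomes and analyses (5.2.2, 6.4.3.2) list craving and consumption, and 6.4.3.2 adds the effects scale and computer tasks. Sip timing is in none of them.

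**The case against.** The strongest case against is that these measures carry little weight. The study is a descriptive feasibility pilot whose main laboratory measure is a drink count, and no before-after comparison of sip timing is specified. Sip onset and offset are also fairly objective on video. All of this stands, and it sets the priority.

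Several stronger readings are tempting, but the document does not support them:

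- **That 6.1.4 rejects assessor blinding because everyone is trained.** It gives no reason, and it sits under the treatment heading after assignment, so it most naturally concerns treatment allocation. On raters the protocol is silent. The gap is the same, but it is an omission and not a decision.
- **That scores would be pushed toward a training benefit.** No section says training should delay the first sip or slow drinking. Section 4.1, on the hypothesis, holds only template instructions, and Section 3.3.1 speaks of reduced drinking. The direction of any bias is therefore unknown.
- **That only sip timing can separate men with equal drink counts.** Section 6.3.5 also plans repeated breath alcohol readings in both sessions and blood alcohol during self-administration. These need no video rater and may plausibly reflect pace.

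Masking also leaves participant expectancy and repeat-session effects in any before-after comparison. That is true, but it is no reason to leave a separate and removable source in place.

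**Conclusion.** The point holds as a cheap, low-priority improvement. Human raters score the pre-training and post-training video, nothing masks them to session, and averaging two raters does not remove a shared expectation. This is a risk of bias, not bias shown to exist.

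On the assumed shifts, the effect on average time per drink is probably small: at most about 3.3% for a shared 30-second shift when four drinks fill the hour. It could be relatively larger for faster drinking or a short time to first sip. The feasibility outcomes and the drink count do not depend on these ratings.

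A reader might infer that the pilot's consumption signal is compromised. It is not, because the drink count does not come from the video scoring. The low-cost judgement assumes that session cues can be removed from the recordings.

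**What to change.** In Section 6.3.5, under Ratings of Drinking Behavior, complete the sentence on the raters and add wording such as:

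> Each recording is split at the two tray deliveries, stripped of date and session labels, and given a random code. The two raters score the segments in random order, masked to session and, if a sham arm exists, to arm. Scoring is done in one batch after data collection and includes recordings from men who leave after Session 1.

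Place a cross-reference to this text in Section 6.1.4. The raters should not have staffed the sessions they score, since otherwise coding does not mask them.

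Do not add a statement that participants are unblinded until Section 6.1.3 has been reconciled with the randomisation or sham wording in Sections 3.2, 6 (step 6), 6.2.1 and 6.3.5. If a sham arm exists, that statement could be wrong and the entry in 6.1.4 would need wider revision.

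The cost is that scoring waits until data collection ends and that 24 recordings, or up to 30 if 15 men start, must be cut and recoded. The number of participants, visits and raters does not change.
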